3. SYNOPSIS

INVESTIGATIONAL PRODUCT	
Name of Investigational Product (IP)	BAX69 (imalumab), a fully human recombinant anti-oxidized macrophage migration inhibitory factor (anti-oxMIF) antibody
Name(s) of Active Ingredient(s)	BAX69 (imalumab)
CLINICAL CONDITION(S)/INDICATION(S)	
Metastatic colorectal cancer (mCRC)	
PROTOCOL ID	391401
PROTOCOL TITLE	A Phase 2a Randomized, Open-Label Study to Assess the Safety, Tolerability, and Efficacy of BAX69 in Combination with 5-FU/Leucovorin or Panitumumab versus Standard of Care in Subjects with Metastatic Colorectal Cancer
Short Title	Phase 2a Study of BAX69 and 5-FU/Leucovorin or Panitumumab versus Standard of Care in Subjects with Metastatic Colorectal Cancer
STUDY PHASE	Ph2a
PLANNED STUDY PERIOD	
Initiation	Q2 2015
Primary Completion	Q4 2016
Study Completion	Estimated study completion will occur when 75% of overall survival (OS) events are reported.
Duration	Approximately 21 months
STUDY OBJECTIVES AND PURPOSE	
Study Purpose The purpose of this study, in subjects with progressive measurable mCRC, is as follows: 
• To evaluate the safety and tolerability of imalumab in combination with 5-fluorouracil (5-FU)/leucovorin (LV) or panitumumab to determine the recommended phase 2 dose (RP2D) of each combination• To compare the efficacy of imalumab in combination with 5-FU/LV versus standard of care (SoC) (investigator choice) as third or fourth treatment line in subjects with KRAS mutated (mut) and/or NRAS mut tumors• To compare the efficacy of imalumab in combination with panitumumab versus SoC (investigator choice) as third or fourth treatment line in subjects with KRAS wild type (wt) and NRAS wt tumors Furthermore, the pharmacokinetic (PK) profile of imalumab in combination with 5-FU/LV or panitumumab will be characterized, and limited pharmacodynamic (PD) serum markers will be explored.	
Primary Objectives 
1. To determine the RP2D of imalumab in combination with 5-FU/LV or panitumumab (Part 1)2. To compare progression-free survival (PFS) between imalumab in combination with 5-FU/LV for subjects with KRAS mut and/or NRAS mut tumors or in combination with panitumumab for subjects with KRAS wt and NRAS wt tumors, versus SoC (investigator choice) as third or fourth treatment line (Part 2)	

Secondary Objectives	

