8.2.2 Part 2: Exploratory Phase 2a

This is a 2-treatment-arm phase using a 2:1 ratio for subjects to receive imalumab + 5-FU/LV or imalumab + panitumumab (Arm A) or SoC per investigator choice (Arm B). Within each stratum, subjects will be randomized in a 2:1 ratio to receive imalumab + 5-FU/LV (KRAS mut and/or NRAS mut tumors) or imalumab + panitumumab (KRAS wt and NRAS wt tumors) (Arm A) or SoC per investigator choice (Arm B). Randomization will occur via an Interactive Response Technology (IRT) System until the targeted number of subjects in each treatment arm is achieved. For each combination in Arm A, subjects will receive imalumab at the RP2D determined in Part 1 for the corresponding combination. Subjects in Arm A with KRAS mut and/or NRAS mut tumors will receive 5-FU/LV in addition to imalumab at the RP2D dose determined in Part 1. Subjects in Arm A with KRAS wt and NRAS wt tumors will receive panitumumab in addition to imalumab at the RP2D dose determined in Part 1. Subjects in Arm B with KRAS/NRAS mut or wt tumors will receive investigator's choice (SoC, including best supportive care). If investigator's choice is to give panitumumab, subjects must have KRAS wt and NRAS wt tumors. All subjects will be treated until disease progression, unacceptable toxicity, or withdrawal of consent.

An independent Data Safety Monitoring Board (DSMB) will review accumulating unblinded safety data of subjects in Part 2 on a quarterly basis. See Section [15.4.2](#) for additional details.

The effect of imalumab in combination with 5-FU/LV or panitumumab on tumor-associated genetic biomarkers will be monitored. Blood and urine samples will be collected from those subjects treated with imalumab in combination with 5-FU/LV or panitumumab who provide consent for this optional exploratory analysis. It is possible that blood/urine biomarkers may correlate with clinical outcome (safety and efficacy) in response to imalumab treatment.

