12.1.2 Assessment of Adverse Events

For the purposes of this study, each non-serious untoward medical occurrence experienced by a subject undergoing study-related procedure(s) before first exposure to IP will be recorded on the AE CRF; however, these events will not be considered as AEs and will not be included in the analysis of AEs.

Each TEAE (non-serious AE or SAE) from the first IP exposure until study completion/discontinuation or 30 days (± 7 days) following the last IP treatment will be described on the AE CRF using the medical diagnosis (preferred), or, if no diagnosis could be established at the time of reporting the AE, a symptom or sign, in standard medical terminology in order to avoid the use of vague, ambiguous, or colloquial expressions (see definition in Section 12.1). Each AE will be evaluated by the investigator for:

- Seriousness as defined in Section 12.1.1.1
- Severity as defined in Section 12.1.2.1
- Causal relationship to IP exposure or study procedure as defined in Section 12.1.2.2.

For each AE, the outcome (ie, recovering/resolving, recovered/resolved, recovered/resolved with sequelae, not recovered/not resolved, fatal, unknown) and if applicable action taken (ie, dose increased, dose not changed, dose reduced, drug interrupted, drug withdrawn, not applicable, or unknown) will also be recorded on the AE CRF. Recovering/resolving AEs will be followed until resolution, medically stabilized, or 30 days after the last IP administration, whichever comes first. If the severity rating for an ongoing AE changes before the event resolves, the original AE report will be revised (ie, the event will not be reported as separate AE). During the course of any AE, the highest severity rating will be reported.

Deviations from the protocol-specified dosage (including overdosing [any dose that is at least 20% higher than the highest explored dose level], underdosing [any dose that is lower than the intended explored dose level by 10%], abuse, and withdrawal [see

Section 9.3]), treatment errors (including incorrect route of administration, use of an incorrect product, and deviations from the protocol-defined dosing schedule), failures of expected pharmacological actions, and unexpected therapeutic or clinical benefits will be followed with regard to occurrence of AEs, lack of efficacy, and/or other observations because these events may be reportable to regulatory authorities.

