12.3 Untoward Medical Occurrences

Untoward medical occurrences occurring before the first exposure to IP are not considered AEs (according to the definition of AE, see Section 12.1). However, each **serious** untoward medical occurrence experienced before the first IP exposure (ie, from the time of signed informed consent up to but not including the first IP exposure) will be described on the AE CRF (and SAER Form if eCRF is not available). These events will not be considered as SAEs and will not be included in the analysis of SAEs.

For the purposes of this study, each non-serious untoward medical occurrence experienced by a subject undergoing study-related procedure(s) before the first IP exposure will be recorded on the AE CRF; these events will not be considered as AEs and will not be included in the analysis of AEs.

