13.2 Datasets and Analysis Cohorts

The Safety Population is defined as all subjects who receive at least 1 administration of IP. The Safety Population will be used for all safety analyses in the trial.

The Full Analysis Set (FAS) will serve as the population for the analyses of efficacy data in the trial. The FAS will include all subjects who 1) received at least 1 administration of IP, and 2) have 1 post-baseline tumor response assessment based on RECIST v1.1 or died within 18 weeks of the start of treatment.

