^b The Safety Follow-up Visit should occur 30 (± 7) days after the last dose of study treatment. For subjects who have stopped study drug or have documented disease progression, post-study telephone calls to assess overall survival will be made by site staff every 3 months.

^c Subject informed consent occurs at screening, prior to any study-specific procedure.

^d IRT will be utilized at screening and baseline visits only for all subjects randomized to Arm B (Part 2) to receive SoC/best supportive care.

^e Vital signs, including body temperature, heart rate, blood pressure, and respiratory rate, are to be measured after a 5-minute rest. Sitting position is recommended for blood pressure measurement. Height and body weight will also be recorded. Weekly monitoring to be done in Cycle 1 only, then Q2W. Vital signs should be evaluated both predose and postdose during treatment with SoC.

^f The 12-lead ECG assessment should be performed predose and 2 (± 1) hours postdose on Day 1 (Baseline, C1D1).

Continued on Next Page

Continued

- ^g Laboratory assessments should be evaluated before drug administration. Immediately prior to Cycle 1, laboratory assessments can be performed either on Day -1 or on Day 1 predose. Hematology tests will be done weekly during each treatment cycle. Chemistry/coagulation tests will be done on Day 1 and Day 15 of each treatment cycle, and Day 8 of Cycle 1 only. Laboratory tests include hematology (complete blood count with differential and platelet counts) and biochemistry (creatinine, creatinine clearance according to Cockcroft-Gault, sodium, potassium, calcium, magnesium, glucose, albumin, alanine aminotransferase, aspartate aminotransferase, alkaline phosphatase, total bilirubin, C-reactive protein, and blood urea nitrogen). Coagulation panel includes International Normalized Ratio and activated partial thromboplastin time.
- ^h Urine dipstick test to be performed on Day 1 of each cycle (prior to dosing), End of Study/Early Termination Visit, and at Safety Follow-up. A serum pregnancy test will be performed to confirm if a positive result is obtained in a dipstick test.
- ⁱ If not readily available, genetic testing for KRAS/NRAS mutation status needs to be done early enough to allow randomization within 4 weeks. If KRAS mutation status is known, the subject can start treatment while NRAS testing is pending.

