4.2 Safety Analysis Set

The Safety Analysis Set is defined as all subjects who receive at least 1 administration of study drug. The Safety Population will be used for all safety analyses in the trial.

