10.2 Analysis of QoL Data

For each QLQ-C30 and QLQ-CR29, the summary statistics of absolute scores and changes from baseline will be calculated for the linear transformed score for Global Health status, functional and symptom scale for the Safety Analysis Set.

For Part 2, the study drug and SoC is compared by a 2-sided Wilcoxon rank sum test with the t-Approximation at an alpha of 0.05.

For each of the 5 dimensions of the EQ-5D, tables will be provided to summarize the frequency and percentage of subjects with no, slight, moderate, and severe problems with or were unable to perform each dimension at baseline and end of study. In addition, the shift in the levels of perceived problems at baseline to the levels of perceived response at end of study will be summarized. The EQ VAS and change from baseline will be summarized by study cohort.

All summary tables will be provided for the study cohorts. Data for all subjects will be included in listings.

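### AE status and the analysis sets depend on exposure to IP or to an undefined study drug, so controls on best supportive care alone have no stated route into the safety, QLQ and PFS comparisons

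*Protocol*

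**What the plan says.** The Protocol synopsis row that begins "Name of Investigational Product (IP" identifies imalumab alone. Protocol 12.1.1 confines an AE to a subject who has been given an IP. Protocol 12.1.2 has each TEAE recorded "from the first IP exposure until study completion/discontinuation or 30 days" after the last IP treatment. Protocol 12.3 adds: "Untoward medical occurrences occurring before the first exposure to IP are not considered AEs". Serious events before IP exposure are likewise kept out of the SAE analysis. Protocol 13.2 continues in the same terms: "The Safety Population is defined as all subjects who receive at least 1 administration of IP". That population serves all safety analyses, and the FAS in the same section has the same first condition.

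The SAP words this differently. Section 4.2 reads: "The Safety Analysis Set is defined as all subjects who receive at least 1 administration of study drug". SAP 4.1 puts the same exposure condition into the FAS. SAP 5.5 lists two departures from the Protocol (no interim analysis, and a new start point for PFS), and the change from IP to study drug is not one of them. SAP 10.2 summarises QLQ-C30 and QLQ-CR29 scores, "functional and symptom scale for the Safety Analysis Set".

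Arm B receives investigator's choice, which Protocol 8.2.2 describes as "SoC, including best supportive care". Table 4 in Protocol 20.2 is the schedule for 4-week SoC cycles and for best supportive care. It collects AEs, and its footnote b says: "The Safety Follow-up Visit should occur 30 (± 7) days after the last dose of study treatment".

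**The concern.** An AE rule keyed to imalumab cannot work for an arm that never receives imalumab. Followed as written, the Protocol gives the control arm no AEs and no safety population, although its own schedules collect AEs in that arm. The SAP wording may bring drug-treated controls back, but only if *study drug* includes SoC drugs. It still says nothing about a control who is given no drug at all.

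At stake is which randomised controls are counted. Membership of the set would depend, in one arm only, on a management choice made by the investigator in an open-label trial, so the comparison would no longer be with SoC as randomised. Comparing QoL between arms is a stated secondary objective, tested with a two-sided Wilcoxon test at 0.05. PFS is the primary endpoint. If the term stays undefined, the control denominator would have to be settled by whoever programs the sets, possibly after data have been seen.

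**Working it through.** **Design figures.** Protocol 13.1 plans 44 imalumab subjects and 22 controls, for 48 PFS events. Schoenfeld's formula with HR 0.565, one-sided alpha 0.15, power 0.80 and 2:1 allocation gives (1.036 + 0.842)² / [(1/3)(2/3)(ln 0.565)²] = 3.527 / 0.0724 = 48.7. The stated 48 is reproduced to within rounding (power 79.6% at 48). No design number is in dispute. The 22 controls are the denominator used below.

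**Tracing the definitions.**

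- Text that excludes Arm B: the AE definition (Protocol 12.1.1), the TEAE recording window (12.1.2), the rule on events before IP exposure (12.3), and the Safety Population (13.2). All are keyed to IP.
- Text that expects Arm B AEs: the TEAE definition, also in 12.1.1, which refers to the treatments; the SUSAR scope (12.1.1.2), which takes in active comparators; AE collection in Tables 4 and 5; AE tabulation by treatment group or arm (Protocol 13.4.4.2, SAP 8.3); and the SoC Mutated and SoC Wildtype cohorts in SAP Table 1 (section 5.4).
- The meaning of *study drug*: SAP 5.3 sets baseline by first administration of imalumab or SoC, which implies that SoC counts. SAP 10.2 compares the study drug with SoC, which implies that it does not.

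**Controls left in the safety set under each reading.**

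- Protocol wording (IP): 0 of 22.
- SAP wording, study drug meaning imalumab regimens only: 0 of 22.
- SAP wording, SoC drugs included: 22 minus the number on best supportive care alone.

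**Size under the third reading.** The documents give no best-supportive-care share, so a range is assumed. With n controls left and 44 imalumab subjects:

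- 95% CI half-width for a difference in AE rates, assuming 30% in both arms: 1.96 × √(0.3 × 0.7/44 + 0.3 × 0.7/n). For n = 22 this is 1.96 × √0.01432 = 23.5 points. For n = 11 it is 1.96 × √0.02386 = 30.3 points.
- QoL difference detectable with 80% power at two-sided 0.05 (normal approximation): (1.960 + 0.842) × √(1/44 + 1/n) SD.

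| Assumed share | Controls left | Half-width (points) | Detectable difference (SD) |
|---|---|---|---|
| 0% | 22 | 23.5 | 0.73 |
| 10% | 20 | 24.2 | 0.76 |
| 20% | 18 | 25.1 | 0.78 |
| 30% | 15 | 26.9 | 0.84 |
| 50% | 11 | 30.3 | 0.94 |

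**FAS.** Protocol 13.2 and SAP 4.1 repeat the exposure condition (IP and study drug respectively). A control on best supportive care alone who fails it for safety also fails it for the primary PFS analysis.

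**The case against.** The strongest reply is that IP is used loosely. The synopsis section on investigational product, dose and administration also lists control drugs and places best supportive care among them. The Protocol FAS has the same IP condition, and it would make no sense in a two-arm PFS comparison if IP meant imalumab only. Protocol 12.1.2.3 requires every SAE during the study to be reported, whether or not related to the IP. Protocol 13.4.1 leaves further detail to the SAP, which uses study drug. This stands as evidence of intent. A reader might infer that Arm B events are settled as non-AEs, or will go unrecorded. The documents do not support that: they contradict themselves, and the schedules do collect the events.

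It can also be said that SoC includes best supportive care, so SAP 5.3 covers these subjects. That is arguable, but no text says what counts as an administration of best supportive care. Conversely, a reader might take the SAP 5.3 baseline rule for undosed subjects as proof that the SAP foresaw these controls and then shut them out. The rule fits equally well with subjects randomised but never treated, whom Protocol 13.4.2 anticipates.

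The consequence is limited in some respects. The safety objective is not comparative and the AE summaries are descriptive. In SAP 10.2 the Safety Analysis Set is named only for the two QLQ instruments, not for EQ-5D, and listings cover all subjects. Protocol 10.3.3.9 places the Safety Follow-up visit after the End of Study visit, so only its 30-day count lacks an origin for these subjects.

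**Conclusion.** The wording is wrong as it stands and needs correcting. The Protocol's IP-based rules exclude all 22 planned controls and conflict with the parts of both documents that require Arm B AEs. The SAP's change to study drug is undefined and is not listed in SAP 5.5. On its most generous reading it still gives a control on best supportive care alone no way into the safety set, the QLQ comparisons or the FAS.

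The number affected is unknown. For an assumed best-supportive-care share of 0% to 50%, 22 to 11 controls remain, and at 0% the SAP wording on that reading costs nothing. The precision figures also rest on the assumed 30% AE rate and a normal approximation.

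A reader might infer that dropping these controls raises the apparent SoC event rate and so flatters imalumab. The documents give no event rates by type of SoC. Controls on best supportive care might have fewer events because they have no drug toxicity, or more because they are frailer. The direction of any bias cannot be stated.

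**What to change.** - Define *study treatment* once, to include SoC drugs and best supportive care.
- For Part 2, define the Safety Analysis Set as all subjects who started assigned management: the first dose for drug regimens, or the C1D1 visit for best supportive care.
- Remove the drug-administration condition for best-supportive-care controls from the FAS in the same way. Otherwise they would enter the safety set but stay out of primary PFS.
- Replace the IP wording in Protocol 12.1.1, 12.1.2, 12.3 and 13.2 to match.
- Apply the definitions in SAP 4.1, 4.2, 8.3 and 10.2, and list the change in SAP 5.5.
- Reconcile Table 4 footnote b, which counts from a last dose, with best-supportive-care subjects, who have none. The timing is for the sponsor to settle.

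The cost is wording in several Protocol and SAP sections. No new visits or data are needed, because Table 4 already schedules the visits and AE collection for these subjects.

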12.4 Non-Medical Complaints

A non-medical complaint (NMC) is any alleged product deficiency that relates to identity, quality, durability, reliability, safety, and performance of the product but **did not result in an AE**. NMCs include but are not limited to the following:

- A failure of a product to exhibit its expected pharmacological activity and/or design function, eg, reconstitution difficulty
- Missing components

- Damage to the product or unit carton
- A mislabeled product (eg, potential counterfeiting/tampering)
- A bacteriological, chemical, or physical change or deterioration of the product causing it to malfunction or to present a hazard or fail to meet label claims

Any NMCs of the product will be documented on an NMC form and reported to the sponsor within 1 business day. If requested, defective product(s) will be returned to the sponsor for inspection and analysis according to procedures.

12.5 Medical, Medication, and Non-Drug Therapy History

At screening, the subject's medical history will be described for the following body systems, including severity (defined in Section 12.1.2.1) or surgery and start and end dates, if known: eyes, ears, nose, and throat; respiratory; cardiovascular; gastrointestinal; musculoskeletal; neurological; endocrine; hematopoietic/lymphatic; dermatological; and genitourinary.

All medications taken and non-drug therapies received from enrollment until completion/termination will be recorded on the concomitant medications and non-drug therapies CRFs.

12.6 Physical Examinations

At screening and subsequent study visits (as described in Table 3, Table 4, and Table 5), a physical examination will be performed on the following body systems: general appearance, head and neck, eyes and ears, nose and throat, chest, lungs, heart, abdomen, extremities and joints, lymph nodes, skin, and neurological. An examination of all major joints will also be performed. At screening, if an abnormal condition is detected, the condition will be described on the medical history CRF. At study visits, if a new abnormal or worsened abnormal pre-existing condition is detected, the condition will be described on the AE CRF. If the abnormal value was not deemed an AE because it was due to an error, due to a preexisting disease (described in Section 12.1.1.5), not clinically significant, a symptom of a new/worsened condition already recorded as an AE, or due to another issue that will be specified, the investigator will record the justification on the source record.

12.7 Clinical Laboratory Parameters

12.7.1 Hematology and Clinical Chemistry

The hematology panel will consist of complete blood count [hemoglobin, hematocrit, erythrocytes (ie, red blood cell count), and leukocytes (ie, white blood cell count)] with

differential (ie, basophils, eosinophils, lymphocytes, monocytes, neutrophils) and platelet counts.

In addition, a serum pregnancy test will be performed on women of childbearing potential at screening.

The clinical chemistry panel will consist of sodium, potassium, calcium, magnesium, albumin, ALT, AST, total bilirubin, alkaline phosphatase, blood urea nitrogen, creatinine, creatinine clearance according to Cockcroft-Gault, C-reactive protein, and glucose.

The coagulation panel will include International Normalized Ratio (INR) and aPTT.

Blood will be obtained for assessment of hematology and clinical chemistry parameters according to the schedule detailed in Section 10.3 (see [Table 3](#), [Table 4](#), and [Table 5](#)). Blood volumes obtained are detailed in [Table 7](#). Hematology and clinical chemistry assessments will be performed on EDTA-anticoagulated whole blood and serum, respectively, at a local laboratory.

